6.4 Duration of Follow Up

The evaluation of the primary and secondary endpoints of ORR, CIR, and DOR are continuous. If in the judgement of patients and the treating clinical team, patients are benefiting from this therapy, the therapy will be continued even after measurement of the primary end-point at week 12 but monitoring will continue every 4 weeks or more often if clinically indicated. Patients will be considered off-protocol monitoring if they develop relapsed or progressive disease.

6.5 Early Stopping Rule for Excessive Toxicity

Bayesian toxicity monitoring (<https://trialedesign.org/one-page-shell.html#BTOX>) will be used to terminate early for excessive toxicity. The maximum allowable probability of Grade ≥ 3 non-hematologic, non-infectious toxicity related to treatment during the induction phase (weeks 1-12) attributed to study treatment, is assumed to be 20% and prior distribution (1,1), then early stopping will occur if the posterior probability that the Grade ≥ 3 non-hematologic toxicity rate exceeds this maximum allowable rate is 80% or greater. The minimum number of patients before stopping 3, cohort size 3, then the study will be stopped early for example, if 2 out of 3, 4 out 9, 7 out of 18, and 12 out of 33 experience SAEs.

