6.0 TREATMENT PLAN

6.1 Treatment Regimen Overview

Administration: Decitabine is reconstituted with 5 ml sterile water to facilitate subcutaneous administration. Decitabine is given by subcutaneous injection. Venetoclax is taken as a tablet prepared by patients pharmacy.

Venetoclax is given at a dose of 400 mg po once per week concurrently with the Decitabine dose (+/- 1 day allowed).

All treatment regimens may be continued indefinitely.

Concomitant Treatment: Hydroxyurea is permitted to control leukocytosis and thrombocytosis. In patients with aggressive high bulk disease as determined by the investigator and PI, may receive debulking chemotherapy with either Gemtuzumab ozogamicin, Cladribine or Cytarabine prior to starting decitabine/venetoclax. Also patients who have mutations in either FLT3 (ITD or TKD), JAK2, IDH1 or IDH2 mutation may receive concomitant inhibitors (as outlined in the table below) at any point during the protocol as determined by the PI. Other than HU and above mentioned drugs, no other concomitant disease modifying therapy is permitted. No additional investigational study is permitted and concurrent participation in other interventional trials are not permitted. Participation in registry or non-interventional studies is permitted.

Mutation	Medication
FLT3 ITD	Midostaurin Gilteritinib Quizartinib
FLT3 TKD	Midostaurin Gilteritinib
IDH1	Ivosidenib Olutasidenib
IDH2	Enasidenib
JAK2	Jakafi

Induction phase: The initial 12 weeks of therapy is considered an induction phase during which dose modifications or holds are discouraged except for severe toxicity severe, non-hematologic adverse events, as per figure study schema. However, if myelosuppression from medications are suspect, treatment holds and dose modifications may be considered in consultation with the study chairs. Desired treatment holds or dose modifications should be reviewed as soon as possible with the study chairs to determine whether dose hold/modification is acceptable. The purpose of the induction phase is to produce relatively rapid reduction of tumor burden to a level that will permit recovery by more functional hematopoiesis that can relieve cytopenias.

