6.1.4 Dose adjustments for hematologic toxicity

The starting dose of decitabine being administered (0.2 mg/kg) and the dose of venetoclax of 400 mg have been identified by previous pharmacokinetic, pharmacodynamic and clinical studies (administering the drugs singly) as the minimal biologically active doses needed to produce the intended therapeutic molecular pharmacodynamic effect. Based on our experience using this regimen, an anticipated side-effect is neutropenia. However, neutropenia is frequently

caused by the myeloid malignancy being treated. Since doses are already minimal biologically active doses, it is important not to prematurely dose-reduce if neutropenia is from disease and not from therapy:

- To avoid premature dose reduction from already minimal biologically active doses, this protocol incorporates an Induction Phase (week 1-12) during which doses should not be held except for clinically exigent circumstances. After the induction phase, the treating clinical team will need to exercise judgement to distinguish between Grade 4 neutropenia ($ANC < 0.5 \times 10^9/L$) caused by disease *vs* treatment, *aided if necessary with repeat bone marrow aspirate and biopsy*.
- If Grade 4 neutropenia is judged to be from treatment, the first step is to hold treatment until recovery of the ANC to $> 0.5 \times 10^9/L$. If neutropenia recurs, then the next step is to decrease decitabine doses by 25% (0.15 mg/kg).
- If neutropenia recurs even on the reduced dose of decitabine, then decrease dose of decitabine by another 25% (0.1 mg/kg). If neutropenia persists even at this dose and is felt to be from treatment and not from disease, treatment should be held until recovery of the ANC to $> 0.5 \times 10^9/L$. Only continue therapy if it is considered to be in the best interests of the patient. Its at discretion of the treating physician based on clinical benefit to the patient, as to when to go back to the full dose of Decitabine or keep at reduced dose.
- To reduce risks from baseline neutropenia caused by the disease, that may deter or hinder administration of potentially beneficial therapy, this protocol permits concurrent administration of G-CSF (filgrastim or biosimilar $\sim 5 \mu\text{g}/\text{kg}$) if thought to be safe by the treating physician

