7.6 Data Safety and Toxicity Committee

It is the responsibility of the PI to ensure that all SAEs occurring on this trial are reported to the Einstein's Cancer Center's Data and Safety Toxicity Committee. This submission is simultaneous with their submission to other regulatory bodies.

The principal investigator is responsible for submitting an annual report to the DSTC as per CCCC Data and Safety Monitoring Plan.

- **7.7 Data and Safety Monitoring Plan (DSMP)**

This protocol will adhere to the policies of the Montefiore/Einstein Cancer Center Data and Safety Monitoring Plan in accordance with NCI guidelines. The principal investigator will review with his co-investigators the data relevant to the safety run-in phase, stopping rules (see sections 6.5 and 6.6) and also for an interim analysis. As outlined in sections 6.5 and 6.6, if 3 or more of the first 6 patients develop Grade 3 or 4 non-hematologic, non-infectious toxicity possibly, probably or definitively related to decitabine or venetoclax, during the induction phase (weeks 1-8) of therapy, then the study will be permanently stopped. During the course of the clinical trial, an interim analysis will be done to monitor the safety

following the accrual of every 3 patients after run-in of 6 patients. The stopping criteria are described for the incidence of Grade 3 or 4 non-hematologic, non-infectious toxicity (SAE). Using Bayesian toxicity monitoring with maximum probability of Grade ≥ 3 non-hematologic toxicity of 0.2, prior distribution (1,1), maximum patients 33, minimum number of patients before stopping 3, cohort size 3, and posterior probability 0.8, we will pause the study for review if 2 out of 3, 4 out of 9, 7 out of 18, and 12 out of 33 experience SAEs.

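### The toxicity stopping rule words its counted event three ways, and under the wording that sets the 20% limit a treatment-related septic death in induction adds nothing to the count

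*Combined protocol and SAP*

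**What the plan says.** Section 6.5 describes the counted event in three ways within one paragraph:

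- The 20% limit applies to Grade 3 or higher "non-hematologic, non-infectious toxicity related to treatment during the induction phase (weeks 1-12) attributed to study treatment".
- The posterior criterion is that the "Grade ≥ 3 non-hematologic toxicity rate exceeds this maximum allowable rate is 80% or greater". The infection exclusion is gone.
- The boundaries apply "if 2 out of 3, 4 out 9, 7 out of 18, and 12 out of 33 experience SAEs".

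The limit "is assumed to be 20% and prior distribution (1,1"), and looks are defined by "The minimum number of patients before stopping 3, cohort size 3".

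Section 7.7 repeats the mixture. It has a run-in rule (3 or more of the first 6 patients, permanent stop) limited to Grade 3 or 4 toxicity with both exclusions, over an induction window given there as weeks 1-8. It then says "The stopping criteria are described for the incidence of Grade 3 or 4 non-hematologic, non-infectious toxicity (SAE"). Next it states the Bayesian rule for non-hematologic toxicity only, and finally gives the boundaries in SAEs. Section 6.5 says the study will be stopped at those boundaries, while 7.7 says it will be paused for review.

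Section 13 continues similar Bayesian monitoring in the expansion phase, citing a section 6.6 that the body of the protocol does not contain.

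Under 7.2.2 an adverse experience that results in death is an SAE. The exceptions there cover laboratory values, some admissions, and admission for uncomplicated neutropenic fever. They do not cover septic or bleeding deaths.

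**The concern.** The protocol itself points to the likely route of serious harm. Section 6.1.4 says "Based on our experience using this regimen, an anticipated side-effect is neutropenia", and section 6.1 says that in induction "dose modifications or holds are discouraged except for severe toxicity severe, non-hematologic adverse events". The sentence that follows in 6.1 does allow holds for suspected treatment-related myelosuppression, in consultation with the study chairs. Infection during neutropenia is therefore a foreseeable serious event in exactly the window the rule covers, yet the wording that defines the limit leaves it out even when it is fatal.

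Nothing else supplies a number:

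- The Simon rule in section 13 counts dose reductions, and a patient who dies of sepsis without one is not clearly counted.
- Section 3.2 replaces patients who miss 12 weeks of therapy for reasons other than progression, so such a patient may also leave the primary-endpoint denominator.
- Infection requiring hospitalization is a secondary endpoint (2.2) with no threshold.
- SAEs go to the monitoring committee, also without a threshold.

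At stake is whether the main safety rule of a tolerability trial planned for up to 85 patients can register treatment-related deaths of this kind.

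**Working it through.** **1. The wordings side by side**

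| Wording | Where | Related septic death counted? | Bleeding death counted? |
|---|---|---|---|
| Non-hematologic and non-infectious, related | 6.5 limit; 7.7 run-in and stopping criteria | No | Undefined |
| Non-hematologic | 6.5 posterior criterion; 7.7 Bayesian sentence | Yes, if classed as an infection | Undefined |
| SAE | 6.5 and 7.7 boundaries | Yes | Yes |

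The protocol does not define non-hematologic, so the bleeding column stays open in the first two rows. The 7.7 run-in and stopping-criteria sentences say Grade 3 or 4, which read literally omits Grade 5.

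**2. The plan's boundaries.** With x events in n patients and a Beta(1,1) prior, the posterior is Beta(1+x, 1+n−x), so P(rate > 0.20) = P(Bin(n+1, 0.20) ≤ x).

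- For 2/3: 1 − 4(0.2³)(0.8) − 0.2⁴ = 0.9728.
- For 4/9, 7/18 and 12/33: 0.9672, 0.9767 and 0.9891.

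All four exceed 0.80, but they are not the smallest counts that do. Those are 1/3 (0.8192), 3/9 (0.8791), 5/18 (0.8369) and 9/33 (0.8746). No single cut-off yields all four printed boundaries: 12/33 requires one above 0.9726 (the value at 11/33), while 4/9 requires one no higher than 0.9672. A 0.95 cut-off gives 2/3, 4/9, 7/18 and 11/33. Both cut-offs are therefore used below.

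**3. What an uncounted death does.** Section 3.2 makes every patient who starts therapy evaluable for safety. Under the definition with both exclusions, a patient who dies of sepsis enters with n raised by 1 and x unchanged. With no other toxicity, the posterior is 0.8⁴ = 0.4096 at 0/3, then 0.1074 at 0/9, 0.0144 at 0/18 and 0.0005 at 0/33. Each such patient moves the rule away from stopping.

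**4. Illustration.** The documents give no rates for these events, so the following are assumptions: 10% countable toxicity and a separate, non-overlapping 15% of treatment-related infectious deaths, 25% together. The 15% would be 0.15 × 33 ≈ 5 patients in the initial phase, or 0.15 × 85 ≈ 13 in all. Stopping probabilities are exact: binomial cohorts of 3, paths removed at the first boundary crossed, looks at n = 3, 6, ..., 84.

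| Boundaries | Deaths excluded (10%) | Deaths counted (25%) |
|---|---|---|
| 0.80 cut-off, to n = 84 | 0.308 | 0.910 |
| 0.95 cut-off, to n = 84 | 0.04 | 0.60 |
| Four printed boundaries only, to n = 33 | 0.03 | 0.31 |

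Of the 0.308, 1 − 0.9³ = 0.271 arises at the first look, where 1 of 3 is enough.

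**5. Cost of counting every death.** If all non-progression deaths were counted regardless of attribution, an assumed background of 5% would raise the counted rate from 10% to 15%. At the 0.80 cut-off, stopping by n = 84 would then rise from 0.31 to 0.50. A 10% background (20% in total) would raise it to 0.73.

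**The case against.** A reader might infer that no wording of the rule lets any number of septic or bleeding deaths trigger it. The documents do not support that. The posterior criterion drops the infection exclusion, and the boundaries count SAEs, which include deaths. On the SAE wording, two septic deaths among the first three patients meet the printed boundary. Bleeding is nowhere classed as hematologic, and the hematologic exception in 7.2.2 concerns laboratory values only.

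A reader might also infer that the trial would run to 85 patients whatever the death rate. That is not supported either. Section 7.7 provides a safety analysis after every 3 patients, SAEs go to the committee, section 13 tabulates whether adverse events resulted in death, and the study chair may suspend or stop the study (6.3). These are opportunities for judgement, not numeric criteria for deaths.

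There is a reason for the exclusion: sections 6.1.5 and 7.2.2 note that infection and neutropenic fever are common in these diseases. That supports leaving out non-fatal events. It is a weaker reason to leave out deaths judged related to treatment.

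Section 13 reports 17 evaluable patients with no safety concerns, so a calculation starting at patient 1 does not describe the risk that remains. This limits what the illustration can claim. It leaves the wording conflict untouched.

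Against the lenient reading, 7.7 places SAE in parentheses after the restricted event, which suggests shorthand, and the posterior clause in 6.5 refers back to the limit defined with both exclusions. The restricted reading is at least as natural as the others.

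**Conclusion.** The concern holds as an ambiguity with a serious consequence under one reading. The counted event is worded three ways. Under the wording that defines the 20% limit and the run-in rule, treatment-related septic deaths in induction contribute nothing. The status of bleeding deaths is undefined, and no other numeric rule monitors induction mortality in either phase.

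Under the assumed rates, counting the deaths raises the probability of stopping by patient 84 from 0.31 to 0.91 at the stated cut-off, or from 0.04 to 0.60 at 0.95. The sizes depend on the invented 10% and 15% rates, on no overlap between the two kinds of event, and on which boundaries are used. The direction does not: under the restricted wording the contribution of these deaths is zero at any rate.

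**What to change.** Use one counted-event definition, in the same words, in 6.5, 7.7 and 13. Keep the exclusion for non-fatal infectious and hematologic events. Count any Grade 5 event in weeks 1-12 that is at least possibly related to study treatment, including infectious, hemorrhagic and hematologic causes. Remove SAE as an alternative name for the event.

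Tabulate all non-progression deaths in weeks 1-12, regardless of attribution, at every look, including those in the expansion phase. Do not add unrelated deaths to the count: the 20% limit was set for treatment-related toxicity, and step 5 of the working shows how quickly a background of such deaths would trigger it.

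In the same edit, reconcile the weeks 1-8 and weeks 1-12 windows, the stop and pause wordings, the reference to section 6.6, and the 0.80 cut-off with the printed boundaries.

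The cost is a few sentences in three sections and one table per look. Reviews or pauses will be triggered somewhat more often, and the attribution of each induction death must be judged and recorded.

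### The toxicity stopping counts listed in Sections 6.5 and 7.7 (2/3, 4/9, 7/18, 12/33) are not the boundaries of the stated rule, which are 1/3, 3/9, 5/18 and 9/33

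*Combined protocol and SAP*

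**What the plan says.** Section 6.5 describes Bayesian toxicity monitoring. The maximum rate "is assumed to be 20% and prior distribution (1,1), then early stopping will occur if the posterior probability" that the rate "exceeds this maximum allowable rate is 80% or greater". The first look is at 3 patients and cohorts are of 3. The section then illustrates the rule: the study stops "if 2 out of 3, 4 out 9, 7 out of 18, and 12 out of 33 experience SAEs".

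Section 7.7 repeats the inputs ("toxicity of 0.2, prior distribution (1,1), maximum patients 33, minimum number of patients before stopping 3, cohort size 3", posterior probability 0.8) and states the action without calling the counts examples: "we will pause the study for review if 2 out of 3, 4 out of 9, 7 out of 18", and likewise at 12 of 33. It adds a run-in rule, "As outlined in sections 6.5 and 6.6, if 3 or more of the first 6 patients" have the defined toxicity "during the induction phase (weeks 1-8) of therapy, then the study will be permanently stopped", and places later looks "following the accrual of every 3 patients after run-in of 6 patients".

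Section 13.0 continues the monitoring into the expansion phase, citing Section 6.6. It reports no safety concerns with 17 patients evaluable after induction.

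**The concern.** A limit, a prior and a cut-off fix the boundary at every sample size, so the printed counts should follow from them. Here they do not, and every listed count is too high. At 5/18 or 9/33, for example, the formula calls for action and the list does not. This is the trial's only numerical toxicity safeguard, and it gives two answers on the same data. The earliest looks have passed without reported concern, so what is at stake is the later looks and the expansion to 85 patients.

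**Working it through.** **Inputs (Sections 6.5 and 7.7).** Limit 0.20, prior Beta(1,1), action at posterior probability 0.80 or more, looks at n = 3, 6, ..., 33.

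**Formula.** With k toxicities in n patients the posterior is Beta(1+k, 1+n−k), and P(rate > 0.20) = P(Bin(n+1, 0.20) ≤ k). By hand for n = 3:

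- k = 1: 0.8⁴ + 4(0.2)(0.8³) = 0.4096 + 0.4096 = 0.819, which already crosses 0.80.
- k = 2: 0.8192 + 6(0.04)(0.64) = 0.973.

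**Listed counts against the stated rule** (posterior probability in brackets):

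| n | Listed count | Smallest count reaching 0.80 | One event fewer |
|---|---|---|---|
| 3 | 2 (0.973) | 1 (0.819) | 0 (0.410) |
| 9 | 4 (0.967) | 3 (0.879) | 2 (0.678) |
| 18 | 7 (0.977) | 5 (0.837) | 4 (0.673) |
| 33 | 12 (0.989) | 9 (0.875) | 8 (0.773) |

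The full set at n = 3, 6, ..., 33 is 1, 2, 3, 4, 5, 5, 6, 7, 7, 8, 9. The run-in rule acts at 3/6 (0.967), where the stated inputs act at 2/6 (0.852).

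**Can another reading reproduce the list?**

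- Different cut-off at 20%: no. For 4/9 to trigger, the cut-off must be at most 0.967. For 12/33 to be the smallest triggering count, it must be above 0.9726, the posterior at 11/33.
- Reading the rule as acting only beyond the boundary: this gives 2/3, 4/9, 6/18, 10/33, which matches the first two only.
- Six other priors, at cut-offs 0.80, 0.90 and 0.95: none matches all four.
- Different limit with Beta(1,1): yes. All four counts and the 3/6 run-in are minimal boundaries for limits of 27.5–30.1% at cut-off 0.80, 26.1–28.7% at 0.85, 24.3–26.3% at 0.90 and 21.8–22.2% at 0.95. At 30% and 0.80, for instance, 7/18 gives 0.818 and 6/18 gives 0.666; 12/33 gives 0.807 and 11/33 gives 0.693.

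**Chance of stopping by 33 patients** (exact recursion in cohorts of 3). The unlisted looks for the printed counts are filled at 30%/0.80: 3/6, 5/12, 6/15, 8/21, 9/24, 10/27, 11/30. The pairs 28%/0.80 and 25%/0.90 give the same fills.

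| True rate | Listed counts | Stated rule | Listed, looks from 6 | Stated, looks from 6 |
|---|---|---|---|---|
| 10% | 4% | 31% | 2% | 14% |
| 20% | 21% | 66% | 18% | 53% |
| 30% | 56% | 91% | 53% | 88% |

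If only the four printed looks are used, the figure at a true 30% is 50%. A mixture of the 3/6 run-in followed by the stated inputs from n = 9 stops 7%, 46% and 85% of the time at true rates of 10%, 20% and 30%.

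**Expansion.** At n = 84 the stated inputs act at 20 events. Inputs that fit the list act at 29 (30%/0.80), 27 (28%/0.80) or 26 (25%/0.90). As an illustration only, since the documents give no toxicity count, suppose 0 to 4 events in the first 18 patients and a true rate of 30% afterwards. The chance of stopping by 84 is then 61–96% under the stated inputs and 2–43% under those three alternatives.

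**The case against.** The best defence is that Section 6.5 offers the counts as examples after giving an explicit formula, and each one does satisfy the formula. Read alone, Section 6.5 is loose rather than false. That does not cover Section 7.7, where the same counts are the trigger and are not called examples.

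Several narrower points stand:

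- The expansion is not without a rule. A formula with fixed inputs defines a boundary at any n. What is missing is printed counts and a working cross-reference, and the maximum of 33 patients in Section 7.7 leaves the scope unclear.
- The 31% chance of stopping at a true 10% rate assumes looks from the third patient. With the Section 7.7 run-in at 3/6 kept, it falls to 7%. The shortfall at a true 30% remains: 85% against 53%.
- A limit near 22% with a cut-off of 0.95 also fits the list, so the counts need not come from a limit close to 30%.
- Section 7.7 does define its use of SAE locally as the Grade 3 or 4 toxicity. Section 6.5 does not, and the general definition in Section 7.2.2 is different.
- Reporting of SAEs to the safety committee and the study chair's power to suspend the study give some protection, but neither replaces a numerical boundary.

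None of this removes the mismatch.

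**Conclusion.** The concern holds and must be fixed. The stated inputs give 1/3, 3/9, 5/18 and 9/33; the listed counts exceed these by 1, 1, 2 and 3 events, and no single cut-off at a 20% limit yields them all. The boundaries are exact and need no outside assumption. The stopping probabilities assume looks every 3 patients, independent outcomes with a constant true rate, and the filled-in boundaries at unlisted looks. On that basis the listed counts cut the chance of stopping at a true 30% rate from 91% to 56%. The documents do not show which inputs produced the list, so it cannot be said whether the inputs or the counts were intended.

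**What to change.** Reconcile Sections 6.5, 7.7 and 13.0 by one of two routes:

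1. Keep the stated inputs and replace the list with 1/3, 2/6, 3/9, 4/12, 5/15, 5/18, 6/21, 7/24, 7/27, 8/30, 9/33.
2. Keep the listed counts and restate the limit and cut-off that they implement.

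Under either route, report the operating characteristics and print the boundary for every look up to 85 patients. With the stated inputs these include 9/36, 12/48, 15/60, 18/75 and 20/84.

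In the same edit, reconcile the following:

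- Section 6.5 stops the study, while Section 7.7 pauses it for review.
- The run-in rule gives induction as weeks 1–8, while Section 6.5 gives weeks 1–12.
- Section 6.5 counts SAEs where it should name the defined toxicity.
- Sections 7.7 and 13.0 cite a Section 6.6 that the current body text does not contain, and the run-in attributed to Section 6.5 is not there.

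The cost is protocol wording and one recomputed table. The first route accepts more frequent stopping when toxicity is low: 31% at a true 10% rate, or 14% if looks start at 6. The second means openly raising the stated limit, or the limit and the cut-off together; raising the cut-off alone cannot reproduce the list. The choice belongs to the investigators and the safety committee.
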